Title:

Does the Use of Pre-operative SSKI Actually Reduce Vascularity and Improve Surgical Outcomes for Total Thyroidectomy in Graves' Disease?

ClinicalTrials.gov ID: NCT04080505

Protocol date: February 23, 2015

Research/Protocol Hypothesis

We hypothesize that the pre-operative use of SSKI (potassium iodide oral solution) reduces the hypervascularity of the thyroid gland in Graves' disease patients undergoing total thyroidectomy, thus reducing blood loss, operative time, and complications.

Scientific Abstract

Patients with Graves' disease who undergo total thyroidectomy are often treated with a 7-14 day pre-operative course of SSKI. This concentrated solution of potassium iodide not only helps to convert patients from a hyperthyroid to euthyroid state, but also is thought to reduce the vascularity of the thyroid gland for surgery. However, there is no published literature evaluating whether there is a true quantitative decrease in vascularity with SSKI treatment. In this prospective, randomized study, we aim to quantify if there is any change in vascular flow with SSKI treatment and if this difference results in a clinically significant difference in surgical outcomes.

Methods

Patients will be randomized into two treatment groups – those who receive SSKI for 7 days before surgery and those who do not. To assess vascular flow within the thyroid gland, all patients will get a baseline neck ultrasound when evaluated in the office, as well as a second ultrasound in the operating room before surgery. Using 3D imaging software, we will quantify the vascular flow in the ultrasound images and compare baseline images with the OR images to assess if there is a difference in vascular flow between these timepoints. Other endpoints we will measure are: estimated blood loss in surgery, total operative time, postoperative complications including rates of recurrent laryngeal nerve injury, hypoparathyroidism, hematoma, infection rates.

Study Description

Study Purpose and Rationale

Patients with Graves' disease and goiters tend to have very vascular thyroid glands, which increases operative bleeding risks/rates. Many surgeons treat these patients with preoperative SSKI which is believed to decrease the vascularity, which in turn may decrease bleeding risks. However, there has been no quantitative data published on whether this is a real effect with true clinical benefit, in either animal or human models with SSKI. There have been some studies in Europe studying Lugol's solution, a different formulation of iodine, which show some decreased vascularity using color Doppler or measurements of CD34 cells (1,2).

Study Design & Procedures

All patients would receive a baseline neck ultrasound on our initial office consultation. We do our own office ultrasounds to assess the pathology ourselves. In this study we would standardize all patients to have a baseline ultrasound with us to obtain vascular flow imaging no less than 7 days prior to surgery.

Patients would be randomized to either receive 7 days of pre-operative SSKI or not receive any drug (in our current practice at Columbia, all patients with Graves' disease receive SSKI pre-operatively, though this is not standard practice across the country, thus the 'no drug' group would be experimental for research). Prescriptions will be written by the surgeon and filled by the patient at an outside pharmacy.

All patients would receive a second ultrasound on the operating table before surgery to assess for change in vascularity (experimental, as not all patients receive intra-operative ultrasounds before surgery). Both ultrasounds are performed by the surgeon and there is no additional charge for this test.

We would record estimated blood loss, operative length, and other complication rates such as recurrent laryngeal nerve injury, hypoparathyroidism, hematoma, infection (these rates are already recorded for all patients).

Any post-operative procedures and data collection will be standard of care. We will review consented patients' chart if there are any post-op complications. If there are no complications, the data collection will be complete at their post-op appointment.

Study Drugs or Devices

SSKI is potassium iodide oral solution. It is a concentrated form of potassium iodide containing 1g/ml. It is commonly used for lung conditions such as emphysema, bronchitis and works as an expectorant. It works by thinning mucous secretions (phlegm) in the lungs.

Saturated solutions of potassium iodide can be used for hyperthyroidism or thyroid storm, as high amounts of iodide temporarily suppress secretion of thyroxine from the thyroid gland.

Ultrasound will be used to take images of thyroid to measure thyroid volumes, as well as take images of the vascular flow in each lobe of the gland.

Using 3D imaging software, we will quantify the vascular flow in the ultrasound images and compare baseline images with the OR images to assess if there is a difference in vascular flow between these timepoints.

Study Subjects

Inclusion criteria: All patients with Graves' disease who will be undergoing total thyroidectomy.

Exclusion criteria: Age less than 18, previous RAI therapy, previous treatment with SSKI.

Our goal recruitment number for this pilot study is 30 patients.

Statistical Analysis

We believe that a decrease in vascularity of at least 10% would be clinically significant. In order to demonstrate this amount of difference, our pilot study would be adequately powered with at least 40 patients to show a difference of 11% between the two treatment arms. Utilizing the program "Power and Sample Size Calculation v 3.0.43", a power analysis was conducted setting type I error at 0.05, Power at 0.8, and an experiment to control arm ratio of 2:1. In order to detect a clinically significant change of 10% vascularity in the gland, 20 patients will need to be included in the experimental arm and 10 patients in the control arm.

References

2. Ansaldo GL, Pretolesi F, Varaldo E, et al Doppler evaluation of intrathyroid arterial resistances during preoperative treatment with Lugol's iodide solution in patients with diffuse

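### Treatment is open, the surgeon prescribes SSKI and performs both scans, and no masking of arm is described for quantifying flow, the outcome behind the sample size; reading coded images would reduce the risk of bias.

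*Combined protocol and SAP*

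**What the plan says.** Study Design & Procedures sets out an open comparison: "Patients would be randomized to either receive 7 days of pre-operative SSKI or not receive any drug". No placebo is described. Under the same heading, "Prescriptions will be written by the surgeon and filled by the patient at an outside pharmacy", and "Both ultrasounds are performed by the surgeon". The first scan is tied to the first visit: "All patients would receive a baseline neck ultrasound on our initial office consultation". The second is done on the operating table, after the treatment period.

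Study Drugs or Devices describes the measurement itself: "Using 3D imaging software, we will quantify the vascular flow in the ultrasound images and compare baseline images with the OR images". The Methods paragraph of the abstract says the same. Neither place names a reader, and neither says that images are coded or that the reader is unaware of arm or timepoint. The rest of the document is also silent on blinding, masking or independent reading.

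The hypothesis is directional: "We hypothesize that the pre-operative use of SSKI (potassium iodide oral solution) reduces the hypervascularity of the thyroid gland". Statistical Analysis bases the sample size on vascularity, using a 10% change with 20 and 10 patients. It also states that "our pilot study would be adequately powered with at least 40 patients to show a difference of 11% between the two treatment arms".

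**The concern.** Flow is the leading outcome and the only one used for sample size. The person who acquires the images can know the allocation, and nothing prevents whoever reads them from knowing it too. An ultrasound flow measurement can be influenced at two points: when the image is acquired, and when an image or region is chosen for quantification.

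A shift at either point that differs between arms passes straight into the between-arm difference. Randomisation balances the patients but does not protect against a measurement error that arises once the arm is known. A shift between office and operating room that is common to both arms cancels in the between-arm comparison. It would still distort the baseline-versus-operating-room comparison that the plan also describes.

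The stake is whether a reported reduction of about 10% could be credited to SSKI, or a null result to its absence.

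**Working it through.** **What can and cannot be checked.** The concern is about design, so there is no stated figure to correct. The plan's 20 + 10 patients for a 10% change cannot be reproduced because no SD is given. The calculation can only be run backwards to the SD it implies, and then used to illustrate what a differential shift would do.

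**Inputs from Statistical Analysis:** type I error 0.05 (sidedness not stated; two-sided used here), power 0.80, ratio 2:1, 20 and 10 patients for 10%, and at least 40 patients for 11%.

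**Assumed inputs:** 10% is read as points of change; the between-arm measurement shift is 2, 3 or 5 points; SD 20 serves as an upper value; there is no true effect; the analysis is a two-sample t-test.

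**Step 1, implied SD.** Solve for the SD at which the noncentral t gives 80% power, with noncentrality = difference / (SD × √(1/n₁ + 1/n₂)).
- 10 points, 20:10: SD 8.90. Check: √(1/20 + 1/10) = 0.3873; 10 / (8.90 × 0.3873) = 2.90, which gives 80% power on 28 degrees of freedom.
- 11 points, 40 patients split 27:13: SD 11.33.
- 11 points, 40 patients split 20:20: SD 12.10.

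The 30-patient and 40-patient statements imply different SDs, so both are carried forward.

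**Step 2, rejection rate with no true effect.** For 20:10, noncentrality = shift / (SD × 0.3873). Both tails are counted against the two-sided 5% critical value on 28 degrees of freedom. Example: a shift of 3 at SD 8.90 gives 3 / 3.447 = 0.87 and a rejection rate of 13.4%.

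| SD (points) | Shift 2 | Shift 3 | Shift 5 |
|---|---|---|---|
| 8.90 | 8.7% | 13.4% | 28.9% |
| 11.33 | 7.2% | 10.1% | 19.6% |
| 12.10 | 7.0% | 9.5% | 17.8% |
| 20 | 5.7% | 6.6% | 9.6% |

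Simulation with 200,000 trials per cell agreed within 0.3 percentage points.

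**Step 3, what masked reading could remove.** It acts only on the part of the shift that arises at reading. If that were half of a 5-point shift (an assumption), 2.5 points would remain.

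| SD (points) | Shift 5 | Shift 2.5 |
|---|---|---|
| 8.90 | 28.9% | 10.8% |
| 11.33 | 19.6% | 8.5% |
| 12.10 | 17.8% | 8.1% |
| 20 | 9.6% | 6.1% |

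**Step 4, which scans are exposed.** The operating-room scan follows the treatment period, so it is taken when the arm can be known. For the baseline scan, the plan gives the consultation visit and a minimum of 7 days before surgery, but not its order relative to randomisation. If it precedes allocation, only the operating-room scan and the readings are exposed; otherwise the baseline scan is exposed too.

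**The case against.** The strongest reply is that bias at reading is inferred from silence. Coding helps only if the reader knows the arm and the software leaves the reader some choice, and the document states neither. It does not say that the surgeon reads the images, nor outright that the prescribing and scanning surgeon are the same person. The best-documented exposure is acquisition in the operating room, which coded reading does not touch. The rates above run from trivial to serious, with nothing in the plan to choose between them. The largest needs a shift of half the target effect. The direction of any bias is also open: the title and rationale read as sceptical of SSKI, and a shift against the drug would cost power, which the illustration does not model. A baseline scan before allocation is the natural reading of the text. Finally, this is a 30-patient pilot.

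Most of this stands as a limit on size. The rates are not evidence that bias will occur, and coding is a partial remedy. It does not answer the omission, though. Open treatment does not require open reading, because stored images can be coded whoever acquired them. If the software is fully automatic, or masking was intended, a sentence saying so would settle the reading step at no cost.

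**Conclusion.** The concern holds. The plan pairs a no-drug comparator with a prescribing surgeon who also scans, and describes no masking of arm or timepoint when flow is quantified. That omission is certain from the text.

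The size of any resulting bias is unknown. Under the stated assumptions, a 2- to 5-point differential shift would turn a 5% error rate into anything from 5.7% to 28.9%, depending on the SD. These figures show sensitivity, not expected harm. The reading part of the concern also assumes that the reader can know the arm and has some choice of image or region. The change should be made because it is cheap and protects the outcome that drives the sample size. Confidence is medium.

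**What to change.** Add to Study Design & Procedures:

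> The baseline scan is obtained before the allocation is revealed. Stored baseline and OR images are exported under a random study code with identifiers, date, location and arm removed. They are quantified in random order by existing study staff, preferably not the operating surgeon, using a written rule for image and region selection. Flow values are locked before they are linked to arm. The same saved flow-imaging settings are used for each patient's two scans where the equipment allows.

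If the software selects and measures regions with no reader input, say so in the same place.

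The cost is a coding sheet, some existing staff time, and quantification delayed to a batch of about 60 scans (30 patients × 2). No treatment, eligibility rule or sample size changes. Two limits remain and should be acknowledged: the surgeon's acquisition in the operating room stays unmasked, and office and operating-room images may still be told apart by appearance.

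### Blood loss is an unmasked estimate with no independent source specified, so a difference between arms could partly reflect observer expectation, by an unknown amount

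*Combined protocol and SAP*

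**What the plan says.** The hypothesis holds that SSKI lowers the vascularity of the gland, "thus reducing blood loss, operative time, and complications". The Methods paragraph ranks these outcomes after vascular flow: "Other endpoints we will measure are: estimated blood loss in surgery, total operative time", followed by complications. Study Design & Procedures repeats the plan to collect them: "We would record estimated blood loss, operative length, and other complication rates". Blood loss is called an estimate in both places, and neither gives a method or an assessor.

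On treatment: "Patients would be randomized to either receive 7 days of pre-operative SSKI or not receive any drug". There is no placebo.

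On who knows the arm: "Prescriptions will be written by the surgeon and filled by the patient at an outside pharmacy". On the imaging: "Both ultrasounds are performed by the surgeon and there is no additional charge for this test". The second of these scans is done on the operating table before surgery.

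On local practice, the section says that at the centre all patients with Graves' "disease receive SSKI pre-operatively, though this is not standard practice across the country". The rationale adds that the drug is believed to lower vascularity and so may lower bleeding risk. It also says that no quantitative data have yet shown this.

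The document says nothing about masking of the surgeon, of operating-room staff or of any outcome assessor.

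**The concern.** Three conditions for observer bias occur together: an outcome that depends on judgement, an allocation known to the surgeon, and a plausible expectation about direction, since the centre gives the drug routinely. Randomisation balances patients at baseline. It does not protect against a difference that enters when the outcome is judged and written down.

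The trial wants to know whether a change in flow carries through to surgical outcomes, and blood loss is the first such outcome in the hypothesis. If the SSKI arm shows less estimated blood loss, a reader cannot separate a drug effect from a tendency to record lower figures in treated patients. In a small trial, a modest tendency of that kind is enough to change how often a comparison reaches significance.

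**Working it through.** **The plan's own figures.** There is none for blood loss: no SD, no effect size, no test. The only sample-size statement concerns vascularity: "a power analysis was conducted setting type I error at 0.05, Power at 0.8, and an experiment to control arm ratio of 2:1", giving 20 and 10 patients for a 10% change. No SD is stated there either, so the figure cannot be reproduced. It can only be inverted. With a two-sided normal approximation, SD = 10 / [(1.960 + 0.842) × √(1/20 + 1/10)] = 10 / (2.802 × 0.3873) ≈ 9.2 percentage points (8.9 with the t distribution). This says nothing about blood loss. Only the arm sizes are carried forward.

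**Inputs for the illustration**
- Arm sizes 20 and 10, from Statistical Analysis. Study Design & Procedures calls the no-drug group experimental, so it is unclear which arm has 20. With equal SDs the calculation is the same either way.
- Significance level 0.05, from Statistical Analysis. Sidedness is not stated; two-sided is assumed.
- True effect on blood loss: zero (assumption).
- Systematic recording shift between arms, b, in SD units: 0.25, 0.50, 0.75 (assumption).
- Two-sample t-test with equal SDs (assumption; no test is specified for blood loss).

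**Formula.** The noncentrality is δ = b / √(1/20 + 1/10) = b / 0.3873. The false-positive rate is the probability that a noncentral t with 28 degrees of freedom and noncentrality δ falls beyond ±2.048.

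| Shift b (SD) | δ | Two-sided rejection rate |
|---|---|---|
| 0 | 0 | 5.0% |
| 0.25 | 0.25 / 0.3873 = 0.65 | 9.6% |
| 0.50 | 0.50 / 0.3873 = 1.29 | 23.9% |
| 0.75 | 0.75 / 0.3873 = 1.94 | 46.4% |

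Nearly all the excess lies in the direction of the shift. At 0.25 SD, 9.1% of trials would reject in that direction, against a nominal 2.5%. The smallest observed difference that reaches p < 0.05 is 2.048 × 0.3873 ≈ 0.79 SD.

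**Sensitivity to size.** Statistical Analysis also mentions at least 40 patients. At 20 versus 20 the same three shifts give 12.0%, 33.8% and 63.7%. A larger trial does not dilute a bias of this kind; it makes the bias more likely to reach significance.

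**What the table does not show.** It does not say that a shift exists here or how large it is. Any 20-versus-10 comparison with these shifts gives these rates. Without a blood-loss SD, the shifts cannot be converted to millilitres.

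**The case against.** The strongest reply is that blood loss is a secondary matter here. The Methods paragraph lists it among the other endpoints, vascular flow is the only quantity with an effect size and a sample size, and the protocol calls the trial a pilot with a goal of 30 patients. No decision rule for blood loss is given. All of this stands, and it limits the weight of the point. It does not remove it, because the hypothesis and the title both put surgical outcomes in play.

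A second reply is that the document never says who makes the estimate. Anaesthesia or nursing staff may already do so. Study Design & Procedures says that rates are already recorded for all patients, although that remark may cover only the complications. This also stands. It is a reason to write the source down, not to leave it open. Similarly, the document does not state outright that the prescribing surgeon is the operating surgeon. It is the natural reading, because the surgeon who prescribes is described in the same terms as the one who scans on the operating table.

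A third reply is that the investigators appear sceptical. The title asks whether the drug actually works, and the rationale notes the lack of quantitative data. The direction of any expectation is therefore plausible but not established.

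A reader might go further and infer that a main claim of the trial can be produced by expectation alone. The document does not support that. Blood loss is not the endpoint on which the trial is sized, the assessor is not named, and nothing in the text gives the size of any recording bias.

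**Conclusion.** The point holds as a weakness in how a hypothesis-named outcome is measured. As written, the plan collects estimated blood loss in a trial without placebo, with the arm known to the surgeon who prescribes and scans, and with no masking or independent source described. This is more than missing detail, because following the plan exactly leaves the outcome open to observer bias.

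The size is unknown. The rates of about 10%, 24% and 46% for shifts of 0.25, 0.50 and 0.75 SD are illustrations. They rest on no true effect, a two-sided t-test at 20 versus 10, equal SDs and assumed shifts. The conclusion is that a difference in blood loss could partly reflect expectation, not that it would. The plan should be changed on this point, but it does not undermine the trial as a whole.

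**What to change.** In Study Design & Procedures, specify the following:

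- The blood-loss endpoint is the figure entered in the routine anaesthesia or nursing record by existing operating-room staff who take no part in randomisation and are not told the arm for the study. It is entered before the surgeon offers an estimate.
- Operative length is taken from the logged start and end times.
- Blood loss is reported as exploratory, with incomplete masking stated as a limitation.

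This leaves prescribing and the information available to the surgeon as they are.

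The cost is a few sentences of protocol text and a small rule on the order of entry in the operating room. The sponsor must first confirm that these records exist, since the document does not mention them. The gain is partial. The routine figure may be rounded, the medication list may reveal the arm to the staff who enter it, and the surgeon's conduct of the operation remains unmasked. Logged times therefore remove recording error from operative length but not any influence of the known arm on how the operation is done.

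### How far complications are followed depends on whether one has already occurred, so late events are under-counted; a common window for all patients would remove the problem

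*Combined protocol and SAP*

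**What the plan says.** Methods lists among the endpoints "postoperative complications including rates of recurrent laryngeal nerve injury, hypoparathyroidism, hematoma, infection rates", and the hypothesis is that SSKI lowers complications. Study Design & Procedures describes how they are collected:

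- On routine recording, it says of the complications "hypoparathyroidism, hematoma, infection (these rates are already recorded for all patients".
- What happens after surgery, including what is recorded, follows usual care.
- The step beyond routine recording has a trigger: "We will review consented patients' chart if there are any post-op complications".
- For everyone else the protocol sets an end point: "If there are no complications, the data collection will be complete at their post-op appointment".

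The last sentence sets an end point only for patients free of complications. The protocol does not give the timing of the post-op appointment, how far the chart review reaches, or a window common to all patients. It describes no masking: one arm receives a drug, the other receives none, and "Prescriptions will be written by the surgeon and filled by the patient at an outside pharmacy".

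**The concern.** The trigger for chart review is any complication, but the endpoints are rates by type. A patient with an early hematoma has the chart opened, and a later infection or hypoparathyroidism could be found there. A patient without an early event has no such review, so the same later event would go unrecorded. If the arms differ in early events, or in how readily an unmasked surgeon records them, they also differ in how many patients are observed beyond the appointment. At stake are the count of late complications and, under those further conditions, the by-type comparison between arms.

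**Working it through.** The protocol gives no expected complication rate and names no test for complications, so there is no figure of its own to reproduce. What follows is an illustration.

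**Inputs**
- From Statistical Analysis: 20 patients in the experimental arm and 10 in control, 30 in all. That section also mentions at least 40; at the same ratio this would scale the counts below by 4/3 and leave the percentages unchanged.
- Study Design & Procedures calls the no-drug group experimental, so the larger arm could be either one. Both cases are shown.
- Assumed: e = risk of a complication by the appointment; l = risk of a later one, independent of e and equal in the two arms except in step 5. Later events are recorded only in patients with an early one. At most one early and one later event per patient.
- Fisher's exact test at two-sided 0.05, 20 v 10, is my choice of test.

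**1. Equal true rates.** Take e = 0.10 and l = 0.10 in both arms. The true any-complication risk is 1 − 0.90 × 0.90 = 0.19. The recorded risk is 0.10 in each arm, so the expected difference is 0. For common recorded rates from 0.02 to 0.40, Fisher's test rejects at most about 3.1% of the time. Type I error is not inflated.

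**2. Unequal early rates.** Take e = 0.10 (SSKI) and 0.30 (no drug), l = 0.10. The recorded later rate is e × l, which gives 0.01 and 0.03 against a true 0.10 in both arms. The true number of later events is 30 × 0.10 = 3.

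| Larger arm | Recorded later events, SSKI + no drug | Missed |
|---|---|---|
| SSKI (20 v 10) | 20 × 0.01 + 10 × 0.03 = 0.5 | 1 − 0.5/3 = 83% |
| No drug (10 v 20) | 10 × 0.01 + 20 × 0.03 = 0.7 | 1 − 0.7/3 = 77% |

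With 20 SSKI and 10 no-drug patients, a test of later events alone would reject 0.2% of the time at l = 0.10, 1.3% at l = 0.20 and 8.5% at l = 0.50.

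**3. Any complication.** The recorded comparison is 0.10 v 0.30, a difference of 0.20. A window ending at the appointment gives the same figures, so the chart-review rule adds nothing here. Full follow-up would give 0.19 v 0.37 (difference 0.18) at l = 0.10, or 0.28 v 0.44 (difference 0.16) at l = 0.20.

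**4. Events summed over the four types.** Recorded events per patient are 0.10 + 0.01 = 0.11 v 0.30 + 0.03 = 0.33, a difference of 0.22. The appointment window (0.10 v 0.30) and full follow-up (0.20 v 0.40) both give 0.20. The distortion is 0.02 in total across all types.

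**5. Equal early rates, real late difference.** Take e = 0.20 in both arms and later rates of 0.05 v 0.15. The recorded later rates are 0.20 × 0.05 = 0.01 and 0.20 × 0.15 = 0.03. A true late difference of 0.10 is recorded as 0.02.

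**The case against.** The strongest reply has four parts.

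- Complications are recorded for every patient as routine, so the trigger does not decide who is assessed up to the appointment. This stands, and it is why the any-complication comparison to that visit is unaffected. It does not equalize observation afterwards, because collection then closes for complication-free patients only.
- The rule is worded identically for both arms. This also stands: step 1 shows no expected difference when the true rates are equal.
- The text does not say that chart review looks for new events; it may only document the complication already known. That is a fair reading, and the by-type distortion depends on the other one. The protocol settles it neither way.
- The stakes are low. "Other endpoints we will measure are: estimated blood loss in surgery, total operative time, postoperative complications" places complications after vascular flow, in a 30-patient pilot sized on vascularity.

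A reader might go further and infer that the rule by itself produces a false advantage for SSKI, citing the threefold ratio of 3% to 1% in step 2. The documents do not support that. The ratio needs a real early difference, or unequal detection, to begin with. It concerns a later-event outcome that the protocol does not define as an endpoint, and it amounts to 0.3 v 0.2 of a recorded event at 10 and 20 patients.

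**Conclusion.** The concern holds in a limited form. Follow-up for complications is triggered by the outcome, with no common window. The surer consequence is under-counting of late events in patients without an early one, and dilution of any true late difference. Unequal observation between arms in the by-type rates is possible only if early rates or detection differ by arm and chart review picks up further events.

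Under the assumed rates, 77% to 83% of later events are missed, while the spurious part of the by-type comparison is about 0.02 in total. None of these rates comes from the documents. This is a minor point for a secondary comparison, worth correcting because correction is nearly free.

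**What to change.** Either of two changes would do.

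1. Review the chart of every consented, randomized patient at the same fixed time after surgery, stated in the protocol, and compare arms on complications within that window. Cost: at most 30 chart reviews.
2. Compare arms only on complications identified from surgery through the post-op appointment, state when that appointment takes place, and use later chart review only to describe how those complications resolved. Cost: a sentence or two, and no between-arm comparison of late events.

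The first is preferable if late events are of interest. In either case the protocol should say what the chart review is meant to capture.

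### Vascularity is to be compared between timepoints, but the trial is sized for a difference between arms; the plan should state a between-arm, baseline-adjusted analysis

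*Combined protocol and SAP*

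**What the plan says.** The comparison of vascular flow is described twice in the same words, in the Methods of the abstract and under Study Drugs or Devices: the investigators will "compare baseline images with the OR images to assess if there is a difference in vascular flow between these timepoints". Study Design & Procedures adds the purpose of the second scan: "All patients would receive a second ultrasound on the operating table before surgery to assess for change in vascularity". None of these sentences refers to arms.

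The design is nonetheless randomised: "Patients would be randomized to either receive 7 days of pre-operative SSKI or not receive any drug". The Statistical Analysis section is a sample-size rationale only. It sets the threshold ("We believe that a decrease in vascularity of at least 10% would be clinically significant"), calls the study "adequately powered with at least 40 patients to show a difference of 11% between the two treatment arms", and then arrives at 20 experimental and 10 control patients for a 10% change, with type I error 0.05, power 0.8 and a 2:1 ratio. It gives no test, model, outcome scale or role for the baseline scan.

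Three further statements bear on the analysis:

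- **Timing and setting.** The first scan is an office "baseline ultrasound with us to obtain vascular flow imaging no less than 7 days prior to surgery", with no upper limit on the interval. The second is on the operating table.
- **Lobes.** The ultrasound will "take images of the vascular flow in each lobe of the gland". No rule reduces this to one value per patient.
- **Arm labels.** Study Design & Procedures says the no-drug "group would be experimental for research", so it is unclear which arm has 20 patients.

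**The concern.** A before-after comparison and a between-arm comparison answer different questions. The two scans differ in place and circumstances and are separated by an open-ended interval. Anything that moves measured flow between office and operating room in all patients enters a before-after test in full. It cancels in a comparison between randomised arms.

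A between-arm contrast is evidently intended, since the trial is randomised and sized for one, but no sentence says that the change will be compared between arms. As written, an analyst could test the SSKI arm before and after, test each arm separately, compare change scores, or adjust for baseline, and could choose after seeing the data. The first two options do not use the randomisation. If either is read as the result, a shift common to both arms can be reported as an effect of SSKI.

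Precision is also at stake. Baseline flow is measured on every patient, and in a trial of 30 leaving it out as a covariate wastes information.

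**Working it through.** **Inputs.** From the Statistical Analysis section: 20 and 10 patients, a 10% difference, alpha 0.05 (taken as two-sided), power 0.80. Not in the documents, and therefore assumed: the SD, the size of any common shift, and the baseline-to-operating-room correlation rho. The 10% is read here as 10 absolute points.

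**The plan's own figure.** Neither sample size can be reproduced without an SD. Solving backwards from 20 versus 10:

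SD = 10 / [(1.960 + 0.842) × √(1/20 + 1/10)] = 10 / (2.802 × 0.3873) = 9.2 points.

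The noncentral t gives 8.9. The sentence on 40 patients and 11% implies a larger SD: 12.1 if split 20:20, 11.3 if split 27:13 (both by t). I use 9.2 as the SD of change and vary it.

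**Step 1: before-after test with no drug effect.** Rejection probability of a two-sided paired t test, with noncentrality = shift × √n / SD. For a shift of 5 this is 5 × √20 / 9.2 = 2.43 with n = 20, and 5 × √10 / 9.2 = 1.72 with n = 10.

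| Common shift (points) | n = 20 | n = 10 |
|---|---|---|
| 0 | 5.0% | 5.0% |
| 1 | 7.5% | 6.1% |
| 2.5 | 21.1% | 12.0% |
| 5 | 63.6% | 33.6% |
| 10 | 99.6% | 86.3% |

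Sensitivity to the SD at a shift of 5: with SD 7, 85.8% (n = 20) and 52.2% (n = 10); with SD 12, 42.4% and 21.9%.

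**Step 2: separate tests in each arm.** At a shift of 5 and SD 9.2, the chance that the 20-patient arm is significant and the 10-patient arm is not is 0.636 × (1 − 0.336) = 0.42. The reverse pattern has probability 0.336 × (1 − 0.636) = 0.12. Both arise with no drug effect, and the imbalance comes only from unequal arm sizes.

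**Step 3: between-arm analyses under the same conditions.** Simulation with 40,000 runs per setting, 20 versus 10, SD 9.2, no drug effect, shifts of 0, 2.5, 5 and 10, and rho of 0.3, 0.5 and 0.7. The change score rejected in 4.9–5.2% of trials and ANCOVA in 4.9–5.1%, at every shift.

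**Step 4: what baseline adjustment adds.** With equal variances at the two visits, the ANCOVA variance relative to the change score is (1 − rho²) / [2(1 − rho)] = (1 + rho) / 2. Taking the change score to have exactly 80% power (SD 8.9 by t):

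| rho | Variance ratio | ANCOVA power, 27 df | Simulated, slope estimated |
|---|---|---|---|
| 0.3 | 0.65 | 93% | 92% |
| 0.5 | 0.75 | 90% | 88% |
| 0.7 | 0.85 | 86% | 85% |
| 0.8 | 0.90 | 84% | 82% |

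**Step 5: scale.** If the 10% is relative, the corresponding difference in log flow is ln(0.9) = −0.105.

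**The case against.** The strongest reply is that the high error rates belong to an analysis nobody has adopted. The trial is randomised, the power statement is about arms, and the natural combined reading is to measure each patient's change and compare it between arms. That analysis holds its 5% level. The no-drug arm is scanned on the same schedule and would reveal a common shift to anyone who looked. On this reading the defect is incomplete wording. In part this stands: the 64% figure applies only if a within-arm test is taken as the result. It does not remove the gap, because no passage states the between-arm comparison. Looking at the control arm's own before-after test is also not a safeguard, as Step 2 shows.

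Second, ANCOVA over a change score is a matter of efficiency, not validity, and the simulated gain shrinks from 12 percentage points at rho 0.3 to 2 at rho 0.8. That stands. The between-arm comparison is essential; the adjustment is a worthwhile, inexpensive addition.

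Third, every magnitude rests on assumption. The SD of 9.2 comes from one of two sample-size sentences that do not agree, it gives 77% power by the t test, and the documents do not say whether the SD behind the calculation is of change or of a single visit. No document supports any particular shift. This also stands, and is why a range is shown. It limits the size of the consequence, not the finding that the analysis is unstated.

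Fourth, the lobe rule, the scale of the threshold and the analysis population are separate omissions. They are minor, but they have to be settled in the same paragraph for the model to be usable.

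**Conclusion.** The concern holds and should be fixed. The only vascularity comparison written down is between timepoints, the sample size rests on a difference between arms, and nothing joins them. Confidence in that reading is high, because it depends only on the text.

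The consequence is conditional. If a before-after test is used and a common shift exists, false attribution to SSKI can be frequent: at 5 points, 42% to 86% in a 20-patient arm as the assumed SD of change runs from 12 down to 7, and 22% to 52% in a 10-patient arm. With no shift the rate is 5%. The documents do not show that a shift exists; the point is that the comparison as written cannot exclude one, while the randomised design can. The power gain from adjustment depends on an unknown correlation and on equal variances at the two visits.

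**What to change.** Add a paragraph to the Statistical Analysis section stating:

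- **Primary analysis.** The between-arm difference in operating-room vascular flow, estimated by linear regression on randomised arm with baseline flow as covariate, reported with a 95% CI. The arm effect is identical if change replaces the operating-room value as outcome in this model, so it still answers the protocol's question about change.
- **Population.** All randomised patients, as assigned, with a stated rule for those who have no operating-room scan.
- **One value per patient.** Both lobes combined, with the rule written out (for example sum, mean or volume-weighted mean).
- **Scale.** Whether the 10% is relative or absolute, with the analysis on the matching scale: log flow and a difference of −0.105 if relative, flow in points if absolute.
- **Within-arm changes.** Reported descriptively only, without tests.

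The same paragraph should give the SD used, and say whether it is of change or of a single visit, so that the sample size can be checked against this analysis. It should also say which arm has 20 patients. The cost is this wording and one degree of freedom; both scans are already planned for every patient, so no new data are needed.
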